The primary outcome is physician billing for ACP (data available directly from Sound Physician-submitted claims with a 1 quarter lag). The primary hypothesis (H1) is that hospital ACP billing practices after distribution of the video game will increase (more than would be expected by secular trends alone). A priori post-hoc hypotheses include: (H2) The larger the proportion of hospital physicians who play the game, the greater the increase in ACP rates, and (H3) Differences in hospital billing practices before-and-after distribution of the video game will be positively associated with the proportion of physicians who have completed their organization's ACP e-curriculum.

The secondary outcomes are episode-based patient healthcare use and mortality (data available from CMS with a 2-year lag).

3. Study Design

Note: All aspects of this study design will need to be re-appraised in light of the evolving Covid-19 pandemic and the associated secular disruptions in hospital medicine staffing, medical decision-making processes, and mortality among older adults.

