	COVID status	dichotomous (0/1)	Based on the presence of an ICD10 diagnosis code or a flag created by the treating physician that the patient was confirmed positive.
hospital covariates	risk-adjusted ACP rate prior to the start of the trial.	continuous	The correlation between risk-adjusted ACP rate and change in ACP rate is 0.23 (and therefore the risk of collinearity is small); these variables capture distinct effects.
	change in ACP rate between Quarter 2 2019 and Quarter 1 2020	continuous	
	practice size	quartiles	
	region	categorical	
	COVID admissions – fraction of total admissions with COVID in the month of the date of admission	continuous	
	COVID prevalence - HRR-level COVID rate in the month of the date of admission	continuous	We will test for collinearity with COVID admissions and exclude based on the variance inflation factor
random effect	hospital	categorical	
Secondary Analysis (Mediation)			
mediator	completion	dichotomous (0/1)	Whether physician finished the Game
	adherence (minutes)	quartiles	Minutes playing the Game

	engagement	quartiles	Physician experience with the game as captured by the Narrative Engagement Scale (scored out of 20)
	change in attitudes	difference in median attitude score before and after exposure	We control for baseline score to separate level effects from change- variable effects
random effect	physician, hospital	categorical	
Secondary Analysis (moderation)			
moderator (hospital and physician- level)	contextual effect – site cooperation rate	continuous	consider as covariate and interaction with MD adherence; remove interaction-effect if not-significant at the 0.05-level
	opportunity – proportion of physicians seen by patient who enrolled in the trial.	continuous	The total number of physicians will be considered as an alternative specification. One additional analysis will be a repeated measures model at the patient level where we define a separate outcome for each physician encountered by the patient until an ACP conversation occurred.
	physician CME compliance	dichotomous	

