### Primary Analysis

Let  $Y_{ijt}$  denote the binary outcome variable (coded as 1 if an ACP conversation occurred and 0 otherwise) for patient  $i$  seen at hospital  $j$  at time  $t$ ,  $Game_{jt}$  a binary variable indicating whether hospital  $j$  has received the Game during period  $t$  ( $Game_{jt} = 1$  if received by hospital  $j$  before or during period  $t$  and 0 otherwise),  $x_{ijt}$  a vector of patient-level covariates,  $z_j$  a vector of hospital-level covariates and  $\theta_j$  a random effect for hospital. The mathematical specification of the statistical model is given as  $Y_{ijt} | \theta_i \sim Bernoulli(\pi_{ijt})$ , where

$$\text{logit}(\pi_{ijt}) = \log \left( \frac{\pi_{ijt}}{1 - \pi_{ijt}} \right) = \beta_0 + \beta_1 t + \beta_2 Game_{jt} + \beta_3 x_{ijt} + \beta_4 z_j + \theta_j$$

where  $\theta_j \sim \text{Normal}(0, \tau^2)$  is the distribution of the hospital-level random effects to account for the fact that the statistical significance of inferences about the effect of the game are likely to be reduced by the clustering of patients in hospitals. The model includes fixed-effects for time-period,  $\beta_{1t}$ , to allow for an unstructured trend across calendar time, which makes the effect of the game (the primary target of inference) to be estimated net of any time-trend. The key coefficient of interest is  $\beta_2$ , which captures the structural shift in the outcome of patients who were enrolled in the study when the hospital receives the iPads, net of general trends across time and other covariates. Because this is a cluster-randomized study, there is a risk that the hospitals in each step are not perfectly balanced, despite attempts to balance these during randomization by forming blocks, and that the distributions of patient characteristics of patients treated by a given hospital may vary across time. To mitigate these concerns, we will adjust for judiciously selected patient and hospital covariates that we hypothesize are reasonably likely to be associated with the outcome. We do not plan to adjust for time-varying hospital-level covariates but we will adjust for whether the hospital was in other programs (e.g., the bundled payment care initiative (BPCI) program) that might influence the culture of the hospital towards ACP; an advantage of adjusting for BPCI participation is that we may obtain more precise inferences.

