#### *Power calculation*

We arrived at our sample size using a combination of feasibility (cost) and assumptions regarding effect size, absent any pilot data about the latter. For each step, we plan to recruit between 25 to 30 physicians from each of 4 to 8 hospitals. Assuming a baseline ACP rate of 22% (rising by 1.5 percentage-points per-quarter), a hospital intra-class correlation (ICC) coefficient of 0.01-0.10, and 160 evaluable patients per physician-quarter, we can detect a 3.5

percentage-point difference between ACP practices before and after the distribution of the intervention using a two-sided test at the 0.05-level with power in excess of 99%, even under the most conservative sample-size assumptions. If we invert the problem to find the smallest effect-size at which our study has 80% power, we find that in the most conservative scenario (76,800 total patients) we can detect a 1.5 percentage-point difference and in the most optimistic scenario (192,000 total patients), we can detect a 1 percentage-point increase.

The method of computing power for this stepped-wedge design follows the commonly used strategy for cluster randomized trials of first determining the design-effect, which can be thought of as a measure of the inefficiency of the given design in comparison to a completely randomized design that is expressed in terms of a ratio of the sample-sizes needed to obtain equally precise estimates, and then applying conventional power calculations. The latter computes power for a two-population comparison using the effective-sample-sizes determined from the design-effect. We estimate the design-effect using the expression in Woertman et al (2013), that was clarified and illustrated in Hemming (2016). Because hospitals may induce correlations in the outcomes of patients who receive care from them, we perform illustrative power calculations that account for the net impact of clustering at the hospital-level. Based on our own prior research and published results of others, we decided that the ICC of hospital is highly likely to be in the range 0.01 to 0.10. The design-effects across the optimistic and pessimistic scenarios ranged between 2.88 and 3.14, implying that for all considered scenarios the stepped-wedge design is about 33% as efficient as a patient-level completely randomized design. The effective sample-sizes (ESS) per group ranged from 30,603 to 12,388 patients per group over the study period (the 5 steps and a baseline period).

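### The primary model assumes one game effect for all hospitals, so its interval for the mean effect over hospitals is too narrow if the effect varies with uptake as H2 expects

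*SAP*

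**What the plan says.** SAP, Primary Analysis, defines a logistic model with fixed period effects, patient and hospital covariates, a binary indicator Game_jt and a hospital intercept θ_j. The target β₂ carries this description: "which captures the structural shift in the outcome of patients who were enrolled in the study when the hospital receives the iPads". It is adjusted for time trend and covariates. The normal distribution of θ_j "is the distribution of the hospital-level random effects to account for the fact that" patients are clustered in hospitals. No other random term and no robust variance is given.

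Protocol section 2 states H2: "The larger the proportion of hospital physicians who play the game, the greater the increase in ACP rates". Participation is opt-in (Protocol section 10), so uptake can differ by site. The SAP's Variable Specification lists site cooperation rate as a continuous moderator, with the instruction "consider as covariate and interaction with MD adherence; remove interaction-effect if not-significant at the 0.05-level". Under Secondary analyses the SAP argues that the game can hardly affect patients if none of the willing physicians plays it, and it plans exposure-dose analyses and an interaction with BPCI participation. All of this is secondary.

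SAP, Power calculation, takes a design effect that depends only on the hospital ICC and then compares two proportions. It reports that "in the most conservative scenario (76,800 total patients) we can detect a 1.5 percentage-point difference", and 1 pp in the optimistic scenario (192,000 patients).

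**The concern.** The plan expects the game to work better at some hospitals than at others, but its primary standard error is computed as if the effect were the same everywhere. A random intercept lets hospitals differ in their level of ACP billing. It does not let them differ in their response to the game. When responses differ, an estimate of the mean response carries a further variance component, roughly the between-hospital variance divided by the number of hospitals. More patients per hospital do not reduce that component. The secondary uptake and dose analyses describe the variation but do not carry it into the interval for β₂.

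What is at stake is the interval for the primary effect. It could claim more precision than the trial has about what the game does at hospitals of this kind, and the overstatement would be largest in the scenario with the most patients.

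**Working it through.** **Inputs.** From SAP, Power calculation: baseline rate 22%, ICC 0.01–0.10, five steps plus one baseline period (six periods), 76,800 or 192,000 patients, two-sided 0.05, 4 to 8 hospitals per step (20 to 40 in all). Protocol section 9 plans 30 hospitals. Assumed, because the documents do not give it: the between-hospital SD of the game effect, η, from 0 to 3 pp.

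**1. The SAP's own figures.** With n patients per hospital-period and ICC r, the stepped-wedge design effect is DE = 6 × [1 + r(6n − 1)] / [1 + r(3.5n − 1)] × 3(1 − r) / [2(5 − 1/5)], and the effective sample size per group is N/(2 DE).

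- 30 hospitals, N = 76,800: n = 76,800/180 = 426.7. At r = 0.01, DE = 3.100 and ESS = 12,388 (SAP: 12,388).
- 40 hospitals, N = 192,000: n = 192,000/240 = 800. At r = 0.01, DE = 3.137 and ESS = 30,604 (SAP: 30,603).

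A two-proportion calculation at 80% power from these ESS values gives 1.49 and 0.95 pp, which round to the stated 1.5 and 1 pp. The SAP's figures are right under a common effect.

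**2. Model-based standard error.** SE_model = √(2 × 0.22 × 0.78 / ESS) gives 0.526 pp (30 hospitals) and 0.335 pp (40 hospitals). Generalised least squares on hospital-period means, with six fixed periods and a random intercept, gives the same values.

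**3. Actual standard error when effects vary.** The planned estimator is a weighted average of the hospital effects. The weights sum to 1 and differ slightly by step, so that J × Σw² ≈ 1.05 for J hospitals. Hence, for the mean over hospitals of this kind:

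SE_true² = SE_model² + 1.05 η²/J, and coverage = P(|Z| < 1.96 × SE_model/SE_true).

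Example with 30 hospitals and η = 2 pp: 0.526² + 1.05 × 4/30 = 0.277 + 0.140 = 0.417, so SE_true = 0.646. Then 1.96 × 0.526/0.646 = 1.60, and coverage is 89%.

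| η (pp) | SE_true, 30 hosp. | Coverage | SE_true, 40 hosp. | Coverage |
|---|---|---|---|---|
| 0 | 0.526 | 95.0% | 0.335 | 95.0% |
| 1 | 0.559 | 93.5% | 0.372 | 92.2% |
| 2 | 0.646 | 89.0% | 0.466 | 84.1% |
| 3 | 0.769 | 82.0% | 0.590 | 73.4% |

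At ICC 0.10 the coverages are 93.4/88.5/81.1% and 92.0/83.2/71.9% at η = 1/2/3 pp. With 20 hospitals and 76,800 patients at ICC 0.01 they are 92.8/86.1/76.8%.

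**4. Coverage for the trial's own hospitals only.** Here only the unevenness of the weights adds variance: SE² = SE_model² + 0.05 η²/J. At η = 2 and 3 pp, coverage is 94.7% and 94.4% (30 hospitals), and 94.5% and 93.8% (40 hospitals).

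**5. Power at 3.5 pp.** The planned test rejects beyond 1.96 × SE_model. At η = 3 pp with 30 hospitals, (3.5 − 1.96 × 0.526)/0.769 = 3.21, so power is above 99%.

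**6. Detectable differences if the effect is proportional to uptake.** Then η = CV × δ, where δ is the mean effect and CV the relative SD of uptake (assumed 0.46–0.86). The planned test's 80%-power difference solves δ = 1.96 × SE_model + 0.84 × SE_true. Check with 30 hospitals and CV 0.86: at δ = 1.52, η = 1.31 and SE_true = 0.580, so 1.96 × 0.526 + 0.84 × 0.580 = 1.52.

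- Planned test: 1.49–1.52 pp (30 hospitals) and 0.94–0.96 pp (40 hospitals).
- By 2.8 × SE_true, which fits a test that uses the actual SE: 1.52–1.65 and 0.96–1.02 pp.

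**Limits.** This is a linear approximation to the logistic model, with equal hospital sizes and no hospital-by-period variation.

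**The case against.** **The target.** Undercoverage arises only if β₂ is the mean over a wider population of hospitals. Protocol section 9 has the hospitals selected rather than drawn at random, and the SAP describes β₂ in terms of enrolled patients. For the average over the trial's own hospitals the planned interval is nearly right (step 4). This stands, and it makes the point conditional on the target. It does not remove it: the SAP models hospitals as random, Protocol section 9 gives generalisability as a reason for choosing the partner, and no sentence limits β₂ to the hospitals sampled.

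**H2 is handled elsewhere.** The Protocol labels H2 a post-hoc hypothesis, and the SAP examines uptake and dose in secondary analyses. A common-effect primary contrast alongside these is not a contradiction. That is fair, but those analyses leave the standard error of β₂ unchanged.

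**No SD is given.** This is true. At 1 pp the loss is only 1 to 3 points, and it becomes material at about 2 pp.

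**The detectable differences.** A reader might infer that 1.5 and 1 pp are too small. The documents do not support that. Both reproduce from the SAP's inputs. Under H2's mechanism the heterogeneity shrinks with the mean effect, so an SD derived at a 3.5 pp mean cannot be carried over to a 1–1.5 pp effect. Step 6 shows that the planned test's figures barely move.

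**A hospital-by-period term might suffice.** In simulations at ICC 0.05 with 400 runs per setting, a hospital-by-period term gave 90–96% coverage and a random game effect 93–97%. The ranges overlap and the Monte Carlo error is about 1 point, so this favours the random game effect only weakly.

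**Conclusion.** The point holds in conditional form. The primary model has no term for variation in the game effect between hospitals, which the trial's own hypothesis expects. If β₂ is read as the mean effect over hospitals of this kind, the 95% interval covers too rarely by an amount that depends on an SD the documents do not give: slight at 1 pp, about 6 points (30 hospitals) to 11 points (40 hospitals) at 2 pp, and 13 to 22 points at 3 pp. For scale, if the mean effect is 3.5 pp and proportional to uptake, an SD of 2 pp corresponds to a relative SD of uptake of 2/3.5 = 0.57, which is also an assumption.

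Three things are not affected: type I error when the game has no effect at any hospital, power at 3.5 pp, and, for practical purposes, the stated detectable differences. The most to be said of 1.5 and 1 pp is that they assume a common effect.

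**What to change.** In SAP, Primary Analysis:

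- State that β₂ targets the mean game effect over hospitals of the kind sampled.
- Add a hospital-specific random game effect (a random slope on Game_jt, correlated with θ_j), or else keep the planned model with a cluster-robust variance. In either case use a small-sample reference distribution suited to 20–40 hospitals.
- Report the estimated between-hospital SD of the effect beside β₂ (from the random-slope model). It bears directly on H2.

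In SAP, Power calculation, one sentence saying that the detectable differences assume a common effect is enough. The figures need not change.

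The cost is one more variance parameter, a slightly wider interval and SAP wording. A test based on the wider interval detects slightly less: about 1.52–1.65 pp and 0.96–1.02 pp at the uptake CVs in step 6. No change to recruitment or data collection is needed.

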As determined by NIH, the DSMB will “1) periodically review and evaluate the accumulated study data for participant safety, study conduct and progress, and, when appropriate, efficacy, and 2) make recommendations to NIDCR concerning the continuation, modification, or termination of the trial. The DSMB considers study-specific data as well as relevant background knowledge about the disease, test agent, or patient population under study.”

As described by NIH, “The DSMB is responsible for defining its deliberative processes, including: event triggers that would call for an unscheduled review, stopping procedures that are consistent with the protocol, unmasking (unblinding), and voting procedures. The DSMB is also responsible for maintaining the confidentiality of its internal discussions and activities as well as the contents of reports provided to it.

The DSMB should review each protocol for any major concern prior to implementation. During the trial, the DSMB should review cumulative study data to evaluate safety, study conduct, and scientific validity and integrity of the trial. As part of this responsibility, DSMB members must be satisfied that the timeliness, completeness, and accuracy of the data submitted to them for review are sufficient for evaluation of the safety and welfare of study participants. The DSMB should also assess the performance of overall study operations and any other relevant issues, as necessary.”

All eligible participants will be contacted at the start of the trial and receive the interventions as described under Section 3. The trial will run for a total of 6 months.

6. Risks & Benefits

Note: Risks may be physical, psychological, social, legal, economic, to reputation, or others.

a. Describe any potential risks, their likelihood and seriousness:

There are two categories of participants in this pragmatic trial: 1) Consented research participants (hospitalists); and 2) Unconsented research participants (patients of participating hospitalists).

The consented research participants are the hospitalists employed by Sound Physicians. A *key consideration in this study that the participants' employer is a partner in conducting the trial.* The primary outcome is the hospitalists' behavior; specifically, the frequency with which hospitalists bill for ACP conversations with patients 65 and older.

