**Statistical Analysis Plan**

**Hopewell Hospitalist: A Video Game Intervention to Increase Advance Care Planning by Hospitalists [Efficacy Trial]**

**NCT 04557930**

**11 November 2021**

## Statistical Analysis Plan

### Variable Specification

Variable type	Variable Name		Variable Format	Notes
Primary Analysis				
dependent variable	primary	acpbilled	dichotomous (0/1)	
	secondary	mortality	dichotomous (0/1)	
		length of stay	continuous	
		7-day readmission	dichotomous (0/1)	
		30-day readmission	dichotomous (0/1)	
	ICU usage	dichotomous (0/1)		
primary predictor	phase of trial at hospital		categorical [0 = pre; 1 = enrollment and post]	We will retain 3-level coding until the point of the analysis (pre 0; enrollment 0.5; post 1)
time	date		categorical with days since start of baseline period as categorical labels	Will capture an anticipated non-linear and differential impact of COVID across time
	block		categorical	Further captures the COVID effect by adjusting for differential time-trends by block. Will allow for heterogeneity as these were pre-formed and control for the same general region of the country.
patient covariates	patient age		categorical variable (65-74, 75-84, 85+)	Association between age and probability of ACP billing is continuous with no inflections at specific ages (based on graphical analysis). We considered using the continuous variable but thought that the categorical variable provides more clinical context (e.g., an OR of 1.02 per year vs. OR 1.32 for patients age 74-85 and OR 1.76 for patients with age 85+)
	Charlson comorbidity index		categorical (0 to ≥5)	

	serious illness (selected based on differences in cohort between pre/post trial period)	dichotomous (0/1)	Serious illness codes based on Kelley et al. "Identifying older adults with serious illness" 2019 J Pain Symptom Management
	illness severity (evidence of organ failure)	exclude for endogeneity	It may be difficult to parse the differences between organ failure and receipt of LST (for example - codes for respiratory failure may be equivalent to the receipt of mechanical ventilation in some institutions). Since we anticipate that stepped-wedge design takes care of differences in cohort, we exclude these codes.
	surprise question	dichotomous (0/1)	Include if available by the time we are ready to submit. Otherwise exclude for missingness.

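### If the game's effect builds up after crossover, the single coefficient β₂ understates it; an exposure-time average should be reported beside it

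*SAP*

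**What the plan says.** SAP, Primary Analysis: the game indicator equals 1 "if received by hospital" in the current period or earlier, and stays 1. Period effects are included "to allow for an unstructured trend across calendar time". Clustering enters through one normal term, which "is the distribution of the hospital-level random effects". The target of inference is β₂, "which captures the structural shift in the outcome of patients who were enrolled in the study when the hospital receives the iPads".

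SAP, Variable Specification: the primary predictor is "categorical [0 = pre; 1 = enrollment and post". Its note adds: "We will retain 3-level coding until the point of the analysis (pre 0; enrollment 0.5; post 1".

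SAP, Power calculation: the design is "the 5 steps and a baseline period", six periods in all, and the last paragraph says the baseline may be extended to three months. Protocol, Section 5: "The trial will run for a total of 6 months". Neither document states the period length; monthly periods are inferred from six periods in six months.

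Neither document plans an exposure-time term, a transition period, or a check for an effect that changes after crossover.

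**The concern.** β₂ describes one immediate and permanent step. The plan gives reasons to expect something less abrupt. The three-level code scores enrollment as partial exposure. Protocol Section 3 has physicians accept first and then receive an iPad by mail. H2 in Protocol Section 2 ties the size of the increase to the share of physicians who play.

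When the effect does depend on time since crossover, a one-coefficient stepped-wedge model with free period effects does not average it. It puts most weight on the first exposed period, where uptake is lowest, and negative weight on the latest ones. At stake is the size of the effect reported for H1: too small if the effect builds up, too large if it fades.

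**Working it through.** **Step 1. Reproduce the SAP's own figures.** Inputs from the Power calculation: k = 5 steps, one baseline period, ICC ρ = 0.01–0.10, 76,800 or 192,000 patients, 22% baseline rate. Splitting the conservative total over 30 hospitals (Protocol Section 9) gives n = 76,800/(30 × 6) = 426.7 per hospital-period. The optimistic total over 40 hospitals gives n = 800. The stepped-wedge design-effect formula the SAP cites, times six periods, is

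DE = 6 × [1 + ρ(6n − 1)]/[1 + ρ(3.5n − 1)] × 3(1 − ρ)/[2(5 − 1/5)].

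For n = 426.7 and ρ = 0.01: 6 × (26.59/15.92) × 0.3094 = 3.10, and 76,800/(2 × 3.10) gives 12,388 per group, as stated. For n = 800 and ρ = 0.01: DE = 3.14 and 30,604 per group (SAP: 30,603). At ρ = 0.10, DE is 2.89. Detectable differences are 1.49 and 0.95 points (SAP: 1.5 and 1). The setting is therefore the SAP's own.

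**Step 2. Weights of β₂ by exposure period.** Let δ(s) be the true effect in the s-th period after crossover. Under generalised least squares with period effects and a hospital random intercept, the expected β₂ is the sum of w(s)·δ(s), and the weights sum to 1. For five sequences and one baseline period, the limit as clustering dominates is w(s) = 6(s − 6)(11s − 35)/840, that is 720, 312, 36, −108 and −120 over 840.

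| Setting (n = 427) | w(1) | w(2) | w(3) | w(4) | w(5) |
|---|---|---|---|---|---|
| Limit | 0.857 | 0.371 | 0.043 | −0.129 | −0.143 |
| ICC 0.01 | 0.835 | 0.367 | 0.050 | −0.117 | −0.134 |
| ICC 0.10 | 0.855 | 0.371 | 0.043 | −0.128 | −0.142 |
| ICC 0.01, 3 baseline periods | 0.718 | 0.344 | 0.085 | −0.059 | −0.087 |
| ICC 0.10, 3 baseline periods | 0.726 | 0.345 | 0.082 | −0.063 | −0.091 |

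If a hospital's effects in different periods correlate at 0.9 instead of 1 (a cluster autocorrelation, CAC, that I assume; the SAP's model implies 1), w(1) is 0.82–0.84 with one baseline period. A linear time term, as the displayed equation might be read, gives the same weights.

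**Step 3. Apply the weights, with full effect = 1.** For half effect then full, the expected β₂ is 1 − 0.5·w(1). At ICC 0.01 that is 1 − 0.5 × 0.835 = 0.58. For linear growth at ICC 0.01: 0.2 × 0.835 + 0.4 × 0.367 + 0.6 × 0.050 − 0.8 × 0.117 − 1 × 0.134 = 0.12. Waning is the mirror image, 1.2 − 0.12 = 1.08.

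| Pattern, periods 1–5 | β₂, 1 baseline period | β₂, 3 baseline periods | Equal-weight average | Average weighted by exposed hospital-periods |
|---|---|---|---|---|
| 0.5, 1, 1, 1, 1 | 0.57–0.59 | 0.64 | 0.90 | 0.83 |
| 0.2 rising to 1 | 0.10–0.12 | 0.19–0.20 | 0.60 | 0.47 |
| 1 falling to 0.2 | 1.08–1.10 | 1.00–1.01 | 0.60 | 0.73 |

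The last column uses weights 5, 4, 3, 2, 1 over 15, because all five sequences reach period 1 and only one reaches period 5. The first row assumes that enrollment lasts one period. The other two rows are illustrations only. A logit fit to expected proportions agrees: for half-then-full it gives 63% of the equal-weight average, against 64–65% here.

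**Step 4. Precision of an exposure-time average.** Fit five exposure levels in place of one and average them equally. For 30 hospitals, 76,800 patients and one baseline period, power for 3.5 points is Φ(3.5/SE − 1.96):

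| ICC, CAC | SE of average (points) | Power |
|---|---|---|
| 0.01, 1 | 0.83 (β₂: 0.53) | 99% |
| 0.10, 1 | 0.83 (β₂: 0.51) | 99% |
| 0.01, 0.9 | 0.97 | 95% |
| 0.10, 0.9 | 1.94 (β₂: 1.21) | 44% (β₂: 82%) |

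The SE ratio is about 1.6 (0.83/0.53; 1.94/1.21). At CAC 1 the average's detectable difference at 80% power is 2.3 points, against about 1.5 for β₂.

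**The case against.** The strongest reply is that nothing in the documents shows an effect that drifts for five periods. The three-level code describes one enrollment phase and then a post phase, so it supports a short ramp and no more. The only persistence evidence, in Protocol Section 1, is that the predecessor game's difference lasted to six months. This stands, and it is why only the first pattern carries the point. That evidence does, however, concern another game and a simulated outcome, and it does not speak to uptake after crossover.

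A reader might infer that the trial would miss a real effect, or that β₂ would land far outside the range of true effects. The documents do not support either as a general statement. Half-then-full gives 0.57–0.59, inside its range of 0.5 to 1. With a 3.5-point average under that pattern, β₂ is expected at 2.2–2.3 points and keeps about 99% power at CAC 1, so the harm is mainly in size. Only the assumed linear growth falls clearly below its range, and waning exceeds its peak by 8–10%. With three baseline periods both sit at about the edge.

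The SAP's Secondary analyses do count the game-playing physicians a patient met, which captures build-up directly. That is useful, but it follows who chose to play, is not randomised, and leaves β₂ as it is.

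Equal weighting is also a choice. The alternative average narrows the gap for the short ramp (0.83 against 0.57–0.59) without closing it. And the fifth exposure level is seen only in the last period, when every hospital is treated, so it leans on the model.

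**Conclusion.** The concern holds in a limited form. β₂ equals the average effect only if the effect is constant from receipt. Under the pattern closest to the SAP's own coding it recovers 0.57–0.59 of the full effect, or about 0.64 with a longer baseline, where a fair average is 0.83–0.90. This rests on five equal steps, equal hospital sizes, the linear form of the model and a one-period enrollment phase; unequal sizes and covariates would shift the weights slightly. The weights are per period, whatever its length.

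Under a constant effect β₂ is unbiased, and under no effect it is a valid test, so H1 is not undermined. A reader might also conclude that an exposure-time model should replace β₂ because the SAP's power is ample. That does not follow: the ample figure depends on constant correlation over time, and at ICC 0.10 with an assumed CAC of 0.9 power falls to 44%. This is a cheap improvement and does not call for a change of primary analysis.

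**What to change.** Keep β₂ as the primary analysis and add one paragraph to the SAP that:

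- states that β₂ assumes a constant effect from receipt of the game, with enrollment counted as exposed;
- pre-specifies one supportive fit of the same model to the same data, with the game effect indexed by periods since crossover (five levels), and states the period length;
- commits to reporting the equal-weight average of the five effects with a 95% CI beside β₂ in every case, with no rule or discretion for switching between the two.

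The cost is one further model fit and the wider interval shown above, which should be described as supportive.
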